6.4. Investigational Product

The investigational products that will be administered using the TDS-IM V1.0 or TDS-ID EP device are the HTNV, PUUV, and HTNV/PUUV DNA vaccines given as a single injection. These investigational products were manufactured by Ajinomoto Althea, Inc., San Diego, California. Table 5 presents a summary description of the investigational products. See the Investigator's Brochure and the Pharmacy Manual for further product information and for detailed vaccine preparation and administration instructions.

Table 5: Investigational Product

Product Name	HTNV DNA Vaccine pWRG/HTN-M(co)	PUUV DNA Vaccine pWRG/PUU-M(s2)	HTNV/PUUV DNA Vaccines
Dosage Form	Liquid	Liquid	Liquid
Unit Dose/Injection Volume	ID: 0.6 mg/0.2 mL IM: 3.0 mg/1.0 mL	ID: 0.6 mg/0.2 mL IM: 3.0 mg/1.0 mL	ID: 1.2 mg (0.6 mg each)/0.2 mL IM: 6.0 mg (3.0 mg each)/1.0 mL
Route of Administration	ID or IM injection deltoid region in alternate arms, if possible	ID or IM injection deltoid region in alternate arms, if possible	ID or IM injection deltoid region in alternate arms, if possible
Physical Description	Clear, colorless solution	Clear, colorless solution	Clear, colorless solution
Manufacturer	Ajinomoto Althea, Inc. San Diego, CA 92121	Ajinomoto Althea, Inc. San Diego, CA 92121	Ajinomoto Althea, Inc. San Diego, CA 92121
Lot Number	1-FIN-2118	1-FIN-2117	1-FIN-2118/1-FIN-2117 ^a
Product Indication	Intended for human use in adults as a prophylactic measure against HFRS	Intended for human use in adults as a prophylactic measure against HFRS	Intended for human use in adults as a prophylactic measure against HFRS

^a A pre-mixed lot of HTNV and PUUV does not currently exist. These will be mixed at the clinical site's pharmacy prior to administration.

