11.7. Selection of Subjects to Be Included in Analyses

All subjects who receive at least one dose of the investigational product will be included in the safety and immunogenicity analysis.

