3.3. Primary Endpoints

The primary endpoints align with the safety objective. The nature, frequency, and severity of adverse events (AEs) and/or serious adverse events (SAEs) associated with TDS-EP-based administration of HTNV and PUUV DNA vaccines.

- The occurrence of solicited local and systemic AEs occurring from the time of each injection through 14 days following the procedure (memory aid to assist with the first 14 days)
- The occurrence of vaccine-related unsolicited AEs from the time of the first injection through 28 days following each injection
- The occurrence of SAEs from the time of the first injection through the final study visit for each subject (approximately 6 months post-last vaccination)
- The occurrence of clinical safety laboratory AEs through 14 days following each study vaccination.

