- Any laryngospasm, bronchospasm, or anaphylaxis within 1 day after administration of study product that is considered related to study product.
- Any generalized urticaria within 3 days after administration of study product that is considered related to study product.
- Serious adverse event related to the study vaccination.
- As deemed necessary by the site principal investigator or appropriate sub-investigator for noncompliance or other reasons.
- Subject refusal of further study vaccination.
- Termination of this trial.
- New information becomes available that makes further administration of the study vaccine unsafe.

All data collected up to the time of withdrawal, including any final evaluation and lab results that may be pending at the time of withdrawal, will be included in the final analysis. All major comparisons between randomized groups will be according to “intent-to-treat” (ITT) principle, that is, participants will be analyzed (and outcomes attributed) according to randomized strategy, regardless of subsequent treatment.

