6.3.1. Safety Population

Subjects who receive at least one immunization will comprise the Safety Population, regardless of subsequent withdrawal from study. If the subject permits, she or he will be followed through resolution of any ongoing adverse events. Women who become pregnant during the duration of the study will be encouraged to seek obstetric care and will be asked to provide follow-up information at the conclusion of the pregnancy. These pregnant subjects will be followed for safety and will not receive any additional immunizations. They will be followed for the duration of their pregnancy, and any evidence of fetal harm will be reported promptly to the UMB IRB and sponsor within 24 hours of study team knowledge.

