TABLE 3.1: Proportion of Seropositive Subjects at Each Blood Collection Time Point

Collection Point	Group 1 (N=X)		Group 2 (N=X)		Group 3 (N=X)		Group 4 (N=X)		Group 5 (N=X)		Group 6 (N=X)	
	n	%	n	%	n	%	n	%	n	%	n	%
1	x	xx										
	[x,x]		[x,x]		[x,x]		[x,x]		[x,x]		[x,x]	
2												
3												
4												
5												
6												
7												

Note: 95% confidence intervals for sample proportion in brackets

TABLE 3.2: Proportion of Subjects that Ever Seroconverted at Each Blood Collection Time Point

Collection Point	Group 1 (N=X)		Group 2 (N=X)		Group 3 (N=X)		Group 4 (N=X)		Group 5 (N=X)		Group 6 (N=X)	
	n	%	n	%	n	%	n	%	n	%	n	%
1	x	xx										
	[x,x]		[x,x]		[x,x]		[x,x]		[x,x]		[x,x]	
2												
3												
4												
5												
6												
7												

Note: 95% confidence intervals for sample proportion in brackets

TABLE 3.3: Duration of Seropositivity if Ever Seroconverted

	Group 1 (n=x)	Group 2 (n=x)	Group 3 (n=x)	Group 4 (n=x)	Group 5 (n=x)	Group 6 (n=x)
Mean						
Standard Deviation						
95% CI for Mean						
1st Quartile						
Median						
3rd Quartile						
Min						
Max						

TABLE 3.4: Geometric Mean Titers of the PsVNA50 at Each Blood Collection Time Point

Collection Point	Group 1 (N=X)		Group 2 (N=X)		Group 3 (N=X)		Group 4 (N=X)		Group 5 (N=X)		Group 6 (N=X)	
	μ	SD										
1	x	x	x	x	x	x	x	x	x	x	x	x
	[x,x]		[x,x]		[x,x]		[x,x]		[x,x]		[x,x]	
2												
3												
4												
5												
6												
7												

Note:

- μ = mean; SD = standard deviation
- 95% confidence intervals for sample proportion in brackets

TABLE 4.1: Safety Analysis Group Comparison: Ever Experienced Solicited Adverse Events

Group:	1	2	3	4	5	6	P-value ¹
N=	x	x	x	x	x	x	
% Reporting	xx	xx	xx	xx	xx	xx	
(95% CI)	(x,x)	(x,x)	(x,x)	(x,x)	(x,x)	(x,x)	
Pair 1	•	•					x
Pair 2		•	•				x
Pair 3				•	•		x
Pair 4	•				•		x
Pair 5		•			•		x
Pair 6		•				•	x
Pair 7			•		•		x

¹P-value obtained from a two-sided Fisher's exact test

TABLE 4.2: Safety Analysis Group Comparison: Ever Experienced Unsolicited Adverse Events

Group:	1	2	3	4	5	6	P-value ¹
N=	x	x	x	x	x	x	
% Reporting (95% CI)	xx (x,x)	xx (x,x)	xx (x,x)	xx (x,x)	xx (x,x)	xx (x,x)	x
Pair 1	•	•					x
Pair 2		•	•				x
Pair 3				•	•		x
Pair 4	•			•			x
Pair 5		•		•			x
Pair 6	•				•		x
Pair 7			•		•		x

¹P-value obtained from a two-sided Fisher's exact test

TABLE 4.3: Immunogenicity Analysis: Ever Seroconverted

Group:	1	2	3	4	5	6	P-value ¹
N=	x	x	x	x	x	x	

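### The intent-to-treat sentence in SAP 4.7 makes no exception for safety, so an adverse event after another arm's product or route would be counted against a regimen the subject did not receive

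*SAP*

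**What the plan says.** SAP 4.7 (Withdrawal) ends with an attribution rule: "All major comparisons between randomized groups will be according to" the intent-to-treat principle, so that "participants will be analyzed (and outcomes attributed) according to randomized strategy, regardless of subsequent treatment". It does not define which comparisons are major and does not set safety apart.

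Safety is the primary objective, and SAP 3.3 says that "The primary endpoints align with the safety objective". SAP Appendix I plans formal safety comparisons between groups. Table 4.1 is titled "Safety Analysis Group Comparison: Ever Experienced Solicited Adverse Events" and Table 4.2 does the same for unsolicited events; each gives pairwise two-sided Fisher p-values. Protocol 11.1.1 also compares adverse event totals between groups by Fisher's exact test.

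The population definitions settle who is included, not the column in which a subject is counted. SAP 6.3.1: "Subjects who receive at least one immunization will comprise the Safety Population, regardless of subsequent withdrawal from study". Protocol 11.7: "All subjects who receive at least one dose of the investigational product will be included in the safety and immunogenicity analysis". SAP Section 8 summarizes adverse events by treatment group without saying whether that means assigned or received. Protocol 9.1 applies intention-to-treat to the initial immunogenicity results and says nothing similar about safety.

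**The concern.** Reactogenicity follows what was injected and with which device, not the allocation list. The primary question is how safe each product is by each route, and attribution by assignment answers a different question whenever the two differ.

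A difference is conceivable here. Six regimens are prepared on site from two vial types of the same concentration and fill volume. Groups 1 to 4 are diluted with saline and Groups 5 and 6 are mixed 1:1; on the combination, Protocol Table 5 notes that "A pre-mixed lot of HTNV and PUUV does not currently exist". The SAP's own deviation table (Table 1.4) has a treatment-administration category that includes incorrectly performed procedures. Administration errors are therefore foreseen, but no rule says how the events that follow them are grouped. A reaction to the combination could be reported under a monovalent arm, or the reverse.

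**Working it through.** No sample size, power or significance level in the documents depends on this rule, so there is no plan figure to reproduce. The check has two parts.

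**Reading the texts together.**
1. The SAP 4.7 rule reaches the major comparisons between randomized groups.
2. Tables 4.1 and 4.2 compare randomized groups on the primary endpoint domain, so they are naturally read as major.
3. SAP 6.3.1, SAP Section 8 and Protocol 11.7 give no competing rule on grouping. Neither document contains an as-received rule.
4. The SAP therefore extends intent-to-treat beyond the one place where the protocol states it.

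**Size for one subject.** Inputs: 12 per group (SAP 4.1); 22 in Group 6 (Protocol 6.3.1); one subject with an event, assigned to A, who received B's regimen.

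Assigned group, x events in 12. As randomized x/12, as received (x − 1)/11:

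x/12 − (x − 1)/11 = (11x − 12x + 12)/132 = (12 − x)/132

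- x = 1: 11/132 = 8.3 points (the maximum)
- x = 7: 5/132 = 3.8 points
- x = 11: 1/132 = 0.8 points
- x = 12: 0

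Group 6, x events in 22: (22 − x)/462, at most 21/462 = 4.5 points.

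Receiving group of 12 with y events: (y + 1)/13 − y/12 = (12 − y)/156, at most 12/156 = 7.7 points.

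For solicited events the high end of x is the likelier one. Protocol 4.4.2.1.2 reports injection-site pain in 28 of 31 subjects (90.3%) in the earlier IM study. At 11 of 12 the shift is 0.8 points.

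**Effect on a Fisher test.** The counts below are assumed for illustration and do not come from the documents. The test is two-sided.

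- As randomized 7/12 vs 1/12, p = 0.0272; as received 6/11 vs 2/13, p = 0.0825
- As randomized 5/12 vs 0/12, p = 0.0373; as received 4/11 vs 1/13, p = 0.1421
- As randomized 6/12 vs 1/12, p = 0.0686; as received 5/11 vs 2/13, p = 0.1819 (no crossing of 0.05)

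One subject can move a p-value across 0.05 but need not.

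**The case against.** **Scope.** The sentence closes the Withdrawal section, straight after a rule on data from withdrawn subjects. There it may have been written with stopped dosing in mind, not a wrong product. A reader might infer that the SAP attributes every outcome, including all adverse event tables, to the randomized group. The text does not go that far: it speaks of major comparisons, and the descriptive tables are left undefined. This narrows the point to Tables 4.1 and 4.2 on the plain reading and leaves a gap elsewhere. It does not remove the point, because the wording covers a wrong product or route and nothing overrides it.

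**Likelihood.** A reader might assume an error rate of 0.1% to 1% over 82 × 3 = 246 injections and obtain 1 − 0.999^246 = 22% to 1 − 0.99^246 = 92% for at least one error. The documents do not support such a figure. They give no rate and report no misadministration, and the range comes entirely from the assumption. It would also count wrong volumes or dilutions that match no other arm and that regrouping cannot repair. A route swap is harder than a mixing error, since IM and ID use separate devices and volumes of 1.0 and 0.2 mL, and staff are not blinded.

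**Size.** A reader might take 8.3 points as the effect of any misdosed subject. It is the maximum, reached only when that subject has the group's sole event.

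**Traceability.** Listing 1.2 describes each deviation by subject and records whether it led to an adverse event. Listings 1.11.1 to 1.11.3 give the dose number. A misattributed event of a kind covered by those listings could be traced. That stands, but the by-group tables and p-values would still carry the wrong attribution.

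**Consequence.** SAP Section 5 calls all analyses exploratory and SAP 6.7 plans no multiplicity adjustment, so no planned decision turns on crossing 0.05. That stands and keeps the priority low.

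**Conclusion.** The point holds as a minor one. As written, SAP 4.7 covers the between-group safety comparisons, departs from the protocol's narrower use of intention-to-treat, and has no as-received counterpart for safety. If a subject were given another arm's regimen, an adverse event that followed would be counted against a regimen not given. The shift in a 12-subject group is (12 − x)/132: 8.3 points at most and near zero for events that almost everyone has. The effect is contingent on a full swap to another arm's product or route, followed by an event. It also rests on reading the comparisons in Tables 4.1 and 4.2 as major, which is the natural reading because safety is primary, but is not spelled out.

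**What to change.** 1. Limit the intent-to-treat sentence in SAP 4.7 to the immunogenicity comparisons, in line with Protocol 9.1.
2. State in SAP 6.3.1 and Section 8 that by-group safety analyses (Tables 2.3.1 to 2.3.4, 4.1 and 4.2) use the product and route actually received. Table 2.2 has no group columns and needs no change.
3. In the tables repeated for each dose (2.3.1 and 2.3.2), use the regimen of that dose.
4. In the ever-experienced Tables 4.1 and 4.2, count a subject with mixed receipt under the regimen received for the majority of doses, and footnote events after a discrepant dose. Under this rule a subject with one wrong dose of three stays in the assigned column, so the shift computed above arises only when most doses, or the only dose, were another arm's. Tables 2.3.3 and 2.3.4, whose mock-ups carry no per-dose note, can follow the same rule. Name a default for subjects with no majority, such as one correct and one wrong dose.
5. Identify these subjects in the existing Listing 1.2; no new listing is needed.

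The cost is a few sentences. No new data are required: the trial is open label, and Protocol 6.4.4 already requires product accountability by subject. The small downside is that the few subjects who move are no longer compared as randomized for safety. The change should be made before database lock, because a later choice of grouping would be made with open-label results in view.

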4.8. Route of Administration, Dosage Regimen, Treatment Period, and Justification

Subjects will receive HTNV DNA vaccine, pWRG/HTN-M(co), and PUUV DNA vaccine, pWRG/PUU-M(s2), administered separately and as a mixture using the TDS-IM and TDS-ID devices developed by Ichor Medical Systems, Inc. Subjects will be randomized (See Section 4.2.1) and will receive 1 dose on each of Days 0, 28, and 56 for a total of 3 doses. The vaccine mixing process will be outlined in a supplementary document.

The rationale for dosages and plan of administration is based on prior work by the delivery device manufacturer and prior experience from a previous HTNV DNA and PUUV DNA vaccine study in which candidate vaccines were shown to elicit antibodies in humans when administered by IM EP.

4.9. Investigational Product

The investigational products that will be administered using the TDS-IM or TDS-ID EP device are the HTNV, PUUV, and HTNV/PUUV DNA vaccines given as a single injection. These investigational products were manufactured by Ajinomoto Althea, Inc., San Diego, California. See the study protocol for further information about the investigational products.

5. SAMPLE SIZE CONSIDERATIONS

Because this is a pilot study, all analyses are exploratory. The group sample sizes of up to 12 subjects thus were chosen without the intention that group differences will be detected with a sufficient power.

6. GENERAL STATISTICAL CONSIDERATIONS

6.1. General Principles

The following descriptive statistics will be reported for all continuous variables: sample size (N), mean, median, standard deviation, first quartile, third quartile, maximum, and minimum. For categorical variables, sample size (N), frequency, and percentage will be reported. In addition, data will be reported overall and by treatment group.

6.2. Timing of Analyses

The final analysis will be performed after database lock.

6.3. Analysis Populations

All subjects excluded from the study analysis will be presented in Table 1.2 and Listing 1.1 in Appendix III.

6.3.1. Safety Population

Subjects who receive at least one immunization will comprise the Safety Population, regardless of subsequent withdrawal from study. If the subject permits, she or he will be followed through resolution of any ongoing adverse events. Women who become pregnant during the duration of the study will be encouraged to seek obstetric care and will be asked to provide follow-up information at the conclusion of the pregnancy. These pregnant subjects will be followed for safety and will not receive any additional immunizations. They will be followed for the duration of their pregnancy, and any evidence of fetal harm will be reported promptly to the UMB IRB and sponsor within 24 hours of study team knowledge.

6.3.2. Immunogenicity Population

Subjects who receive at least one immunization and for whom serological data are available will comprise the Immunogenicity Population. If a subject withdraws from the study, all data collected up to the time of withdrawal, including any final evaluation and lab results that may be pending at the time of withdrawal, will be reported. Likewise, any specimens collected up to the time of withdrawal, including any samples collected for storage and use in future research, will be kept and utilized as outlined in the protocol and consent form. A subject may, however, choose to revoke consent for the use of her or his samples, whereby any unused samples will be destroyed.

6.4. Missing Data

No imputations for missing data are planned. For analyses that require study completion, such as the final overall rate of seroconversion for all subjects, subjects who withdrew before the study completion will be excluded.

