7.5. Termination of Dosing and/or Subject Withdrawal Criteria

Termination of dosing is defined as someone who elects to no longer receive doses but is willing to remain on the study for continued observations, immunogenicity assessment and monitoring of safety parameters. Withdrawal from study is defined as not participating in this study any longer, and not continuing to be observed by the study physician. Each subject may withdraw consent for continued dosing or from the study at any time without penalty. Counseling about the subject's health will be provided if he/she decides to discontinue participation in the study. Medical advice regarding what is in the best interest of the subject will be provided.

The PI may discontinue the subject's receipt of investigational product without the subject's consent if any of these criteria is met:

1. The discovery or development of any health condition within a subject that would make his or her continued participation in the protocol dangerous to him- or herself.
2. The failure of the subject to comply with the requirements of the protocol.
3. The scientific integrity of the study may be compromised by further participation.
4. Any significant finding that in the opinion of the investigator would increase the risk of the subject having an adverse outcome from further participation in the study.

For example:

- Pregnancy
- Receipt of disallowed licensed vaccine, experimental product or medication
- New onset of illness or condition that meets the Exclusion Criteria
- Medical condition or medication change for which continued participation, in the opinion of the site principal investigator or appropriate sub-investigator, would pose a risk to the subject or would likely confound interpretation of the results
- Presence of signs or symptoms that could confound or confuse assessment of study vaccine reactogenicity
- Grade 3 solicited or unsolicited adverse event that is ongoing, whether or not it is improved or resolving. An unresolved or continuing Grade 1 or Grade 2 adverse event is permissible following the documented determination by the site principal investigator or appropriate sub-investigator, that it would not render study vaccination unsafe or interfere with the evaluation of adverse events or immunologic response
- Grade 3 solicited or unsolicited adverse event that occurs without alternative etiology in the 7 days following study vaccination

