7.5.2. Termination of Dosing

Subjects who do not receive all 3 vaccinations will be encouraged to remain in the study and complete study visits for follow-up, safety and immunogenicity assessments per the Study Events Schedule (Table 4). If the scheduled visit does not include collection of blood for safety or immunogenicity, the visit may be conducted by phone call/ electronic communication (eg, e-mail, text message) rather than in person.

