3.4. Secondary Endpoints

The secondary endpoints align with the immunogenicity objectives.

Secondary endpoints, correlating to the secondary objectives of the study will be to determine the proportion of seropositive subjects ($\text{PsVNA50} \geq 1:20$) and the final overall rate of seroconversion over all scheduled time points to study completion for each study group. GMT will be calculated using PsVNA50.

- Determination of the proportion of seropositive subjects (defined as $\text{PsVNA50} \geq 1:20$) at each scheduled time point (eg, Days 0, 28, 56, 84, 140, and 220)
- Determination of the final overall rate of seroconversion over all scheduled time points to study completion for each study group. Seroconversion is defined as a post-vaccination HTNV- or PUUV-specific titer of $\geq 1:40$, or a minimum four-fold rise compared to baseline titer, and all study volunteers will begin the study with a baseline titer < 20 (ie, seronegative).
- Determination of GMT of the PsVNA50 for HTNV- and PUUV-specific neutralizing antibodies at each scheduled time point for each study group and over all time points for each study group.

Exploratory endpoints:

Exploratory endpoints, evaluated as part of the immunogenicity objectives, including calculation of PsVNA80 titers for HTNV and PUUV may be calculated from the collected data for informational purposes, and neutralization assays using other hantavirus PsV (eg, Seoul virus, Dobrava virus) may also be performed to evaluate levels of cross-neutralizing antibodies.

- Determination of GMT of neutralizing of the PsVNA80 for HTNV- and PUUV-specific neutralizing antibodies at each scheduled time point for which blood samples are taken for each study group and over all time points for each study group
- Determination of GMT of neutralizing of the PsVNA50 and 80 for Seoul- and Dobrava-specific neutralizing antibodies at each scheduled time point for which blood samples are taken for each study group and over all time points for each study group

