4.7. Withdrawal

Termination of dosing is defined as someone who elects to no longer receive doses but is willing to remain on the study for continued observations, immunogenicity assessment and monitoring of safety parameters. Withdrawal from study is defined as not participating in the study any longer, and not continuing to be observed by the study physician. Each subject may withdraw consent for continued dosing or from the study entirely at any time without penalty. Counseling about the subject's health will be provided if he/she decides to discontinue participation in the study. Medical advice regarding what is in the best interest of the subject will be provided.

The PI may discontinue the subject's receipt of investigational product without the subject's consent if any of these criteria is met:

- The discovery or development of any health condition within a subject that would make his or her continued participation in the protocol dangerous to him- or herself.
- The failure of the subject to comply with the requirements of the protocol.
- The scientific integrity of the study may be compromised by further participation.
- Any significant finding that in the opinion of the investigator would increase the risk of the subject having an adverse outcome from further participation in the study.

For example:

- Pregnancy
- Receipt of disallowed licensed vaccine, experimental product or medication
- New onset of illness or condition that meets the Exclusion Criteria
- Medical condition or medication change for which continued participation, in the opinion of the site principal investigator or appropriate sub-investigator, would pose a risk to the subject or would likely confound interpretation of the results.
- Presence of signs or symptoms that could confound or confuse assessment of study vaccine reactogenicity.
- Grade 3 solicited or unsolicited adverse event that is ongoing, whether or not it is improved or resolving. An unresolved or continuing Grade 1 or Grade 2 adverse event is permissible following the documented determination by the site principal

investigator or appropriate sub-investigator, that it would not render study vaccination unsafe or interfere with the evaluation of adverse events or immunologic response.

- Grade 3 solicited or unsolicited adverse event that occurs without alternative etiology in the 7 days following study vaccination.

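### SAP 6.4 excludes withdrawn subjects from the overall seroconversion rate, contradicting Protocol 9.1 and other SAP sections, so the denominator of the rate is unsettled

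*SAP*

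**What the plan says.** **The exclusion.** SAP 6.4 plans no imputation. For analyses that it says require completion, it continues: "such as the final overall rate of seroconversion for all subjects, subjects who withdrew before the study completion will be excluded".

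**The endpoint.** SAP 3.4 words it as "Determination of the final overall rate of seroconversion over all scheduled time points to study completion for each study group". Seroconversion there is a post-vaccination titer of at least 1:40 or a four-fold rise from baseline. Table 3.2, Table 4.3 and Figure 1.2 are titled in terms of having ever seroconverted.

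**Sections that keep withdrawn subjects.**
- SAP 4.7 retains data up to withdrawal, including results "pending at the time of withdrawal, will be included in the final analysis". It then says "All major comparisons between randomized groups will be according to" the intent-to-treat principle.
- SAP 6.3.2: "Subjects who receive at least one immunization and for whom serological data are available will comprise the Immunogenicity Population".
- SAP 9 lists the final overall seroconversion rate among the variables analysed on eligible, vaccinated subjects with serology. It sets no completion requirement.
- Protocol 11.7 includes everyone with at least one dose.
- Protocol 9.1 sets an order. The initial analysis takes all subjects with at least one dose, a pre-vaccination sample and at least one valid post-vaccination sample, as assigned and regardless of completion. Completers with serology are analysed afterwards.

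**Who counts as withdrawn.** SAP 4.7 separates the two ways of stopping: "Termination of dosing is defined as someone who elects to no longer receive doses but is willing to remain on the study". Protocol 7.5 says "Withdrawal from study is defined as not participating in this study any longer". Protocol 7.5.2 adds that "Subjects who do not receive all 3 vaccinations will be encouraged to remain in the study and complete study visits".

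**The concern.** An endpoint that asks whether a subject ever converted is settled at the first qualifying titer. Nothing seen later can undo it, so a converter who leaves has no missing outcome and counting that conversion needs no imputation. The no-imputation policy therefore gives no reason to drop the subject.

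SAP 6.4 is the only sentence that says how withdrawals are handled for this particular rate, and it matches only the second of the two analyses in Protocol 9.1. Two analysts following different SAP sections could report different rates from the same data. The overall rate and the ever-seroconverted tables could also end up on different sets, because SAP 6.4 does not say whether it governs Tables 3.2 and 4.3 and Figure 1.2.

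The rate is one of the measures named in SAP 3.2 for identifying the most immunogenic combination and route. If leaving is related to response, groups could shift by different amounts.

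**Working it through.** **Inputs.** Twelve enrolled per group so that about 10 complete (SAP 4.1 and 4.3), hence an allowance of 2 leavers in 12. Two-sided alpha of 0.05 (Protocol 11.3). Benchmark of 7/10 or 8.4/12 converters to establish a true rate of at least 30% (Protocol 11.2). The numbers of converters, and which leavers had converted, are assumptions; the documents do not give them. Leavers are assumed to have at least one valid post-dose sample.

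**1. Reproducing the plan's benchmark.** Exact (Clopper-Pearson) two-sided 95% lower bound, with n subjects and x converters: the 2.5% point of Beta(x, n − x + 1).
- n = 10: 6/10 gives 26.2% (below 30%); 7/10 gives 34.8% (above). The stated 7/10 is reproduced.
- n = 12: 7/12 gives 27.7% (below); 8/12 gives 34.9% (above). The exact threshold is 8; the printed 8.4 is 70% of 12.

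**2. Same 12 subjects, 8 observed converters, 2 leavers.** All dosed: 8/12 = 67% (35–90%). With k of the 2 leavers being converters, SAP 6.4 reports (8 − k)/10. The true ever-converted proportion in these 12 lies between 8/12 and (8 + 2 − k)/12, since only leavers without a conversion are unresolved.

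| k | SAP 6.4 rate (exact 95% CI) | Range for the 12 |
|---|---|---|
| 0 | 8/10 = 80% (44–97%) | 67–83% |
| 1 | 7/10 = 70% (35–93%) | 67–75% |
| 2 | 6/10 = 60% (26–88%) | 67% exactly |

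In the last row the SAP 6.4 figure is below a rate already observed in full.

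**3. If withdrawal is random.** There are 66 ways to choose 2 leavers from 12. The probabilities are 6/66 = 9% for k = 0, 32/66 = 48% for k = 1 and 28/66 = 42% for k = 2. The mean SAP 6.4 rate is (6 × 0.80 + 32 × 0.70 + 28 × 0.60)/66 = 44/66 = 67%. There is no average bias, only lost observations and precision.

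**4. Effect on the Protocol 11.2 benchmark.**
- Seven converters among 10 completers and two leavers without conversion: 7/10 meets 30% (lower bound 34.8%); 7/12 does not (27.7%).
- Six converters among 10 completers and two leavers who had converted: 6/10 does not (26.2%); 8/12 does (34.9%).

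The choice of denominator can change the reading in either direction.

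**The case against.** **A completer rate is partly planned.** The endpoint runs to study completion, and Protocol 9.1 does plan a completer analysis. This stands: reporting the completer rate is not itself an error. What is wrong is that SAP 6.4 prescribes it without ranking it behind the inclusive analysis, which the protocol puts first.

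**A reader might infer that SAP 6.4 removes the intent-to-treat version, leaving completers only.** The documents do not support that. SAP 9 lists the same rate on a set with no completion requirement, SAP 4.7 keeps data up to withdrawal, and SAP 1 asks for the SAP and protocol to be read together. The result is a contradiction, not a deletion.

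**A reader might also infer that anyone who misses a dose is dropped.** That does not follow. Stopping doses is defined separately from withdrawal, and those subjects stay in follow-up.

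**Day 220.** If completion meant Day 220, a subject with every serum to Day 140 who then left could be excluded. But the SAP lists Day 220 as a serology time point, so within the SAP completion and last serum coincide. The gap appears only against the current protocol, where the last serum is Day 140 and Day 220 is a telephone call. It is a version mismatch to correct in the SAP update.

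**The illustration is assumed and the intervals overlap widely.** True. It shows what the rule can do, not what it will do.

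**Keeping unconverted leavers in the denominator resembles non-responder imputation, while both documents plan none.** This stands in part. Protocol 9.1 fixes the set, not this counting rule, so the rule has to be declared and the result labelled as a proportion observed to convert.

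**Conclusion.** The contradiction is real and should be fixed before database lock. SAP 6.4 discards known conversions in subjects who later withdraw, and it conflicts with Protocol 9.1 and 11.7 and with SAP 4.7, 6.3.2 and 9. The denominator of the overall rate is contradictory, and possibly that of Tables 3.2 and 4.3 and Figure 1.2 as well.

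At the planned allowance of 2 leavers in 12 and an assumed 8 converters, the reported rate can be 60%, 70% or 80% against 67% observed, and the Protocol 11.2 benchmark can be met or missed depending on the set. The direction cannot be known in advance. A reader might infer a systematic bias, but that would require withdrawal to be related to response, which the documents do not establish.

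The importance is moderate. The endpoint is secondary, SAP 5 calls all analyses exploratory, and Protocol 11.2 disclaims a design for significant group differences. Per-visit seropositivity and titers are not named in SAP 6.4.

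**What to change.** 1. Delete the exclusion in SAP 6.4.
2. Use the initial set of Protocol 9.1 as the main denominator for the overall seroconversion rate, Tables 3.2 and 4.3 and Figure 1.2. Align SAP 6.3.2 and 9 with it; as worded, 6.3.2 does not ask for a post-vaccination sample.
3. Count any observed post-vaccination seroconversion. State whether serum from the early termination visit (Protocol, Early Termination Visits) counts, since it need not fall at a scheduled time point.
4. State that the result is the proportion observed to seroconvert. Leavers without an observed conversion stay in the denominator, so it is a lower bound for the true rate. Print their number beside each group's rate so that the upper bound can be read off.
5. Report the completer rate as supportive, as Protocol 9.1 plans. Tie completion to the last scheduled serum (Day 140 in the current protocol) and update the SAP's Day 220 serology to match.

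Cost: wording edits to SAP 6.3.2, 6.4 and 9 and to the serology schedule, one count per group and one supportive row. No new data are needed. The downside is that the main rate becomes somewhat conservative where early withdrawal is common; the printed count makes that visible.
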